### 3.7.8 *Echocardiogram*

Echocardiogram results will be listed.

### 3.7.9 *Concomitant Medications*

All medications will be coded by WHODrug (Version Mar2014). Medications start and stop dates that are recorded on the Prior and Concomitant Medications CRF will be used to determine whether the medications are prior or concomitant to the treatment period. Missing or partial dates will be imputed as outlined in Section 3.7.1. Prior medications include medications started prior to the first dose of Study Drug regardless whether continued while on treatment or not. Concomitant medications include medications that patients exposed to on or after the first dose of Study Drug. A prior medication with an imputed stop date that is missing or on or after date of first dose of Study Drug will also be considered as a concomitant medication. Medications will be classified based on (imputed) start and (imputed) stop dates as follows:

#### 1) Prior Medication

Start Date	End Date
< FDD	Any non-missing stop date
	Missing

FDD = Date of First Dose of Study Drug

#### 2) Concomitant Medication

Start Date	End Date
< FDD	$\geq$ FDD
	Missing
$\geq$ FDD	Any non-missing stop date
	Missing

FDD = Date of First Dose of Study Drug

Medication verbatim terms will be coded to Anatomical Therapeutic Chemical (ATC) classification and preferred name using the World Health Organization Drug Dictionary (Version Dec 2014).

Prior and concomitant medications will be summarized separately for each analysis period by ATC class, preferred name, treatment group and overall with counts and percentages, sorting by decreasing frequency in the overall column.

Additionally, antidiabetic medication changes during each analysis period, which include those medications that are started, stopped, or changed dose during the analysis period, will be summarized by ATC class, preferred name, analysis period, treatment group and overall with counts and percentages for the SAF1 and SAF2, sorting by decreasing frequency in the overall column.

Prior and concomitant medications will be displayed in patient listings for all randomized patients. Note that imputed dates will be used for prior and concomitant medications classification. Originally reported dates will be used for listings.

### **3.7.10 MRIs**

The hepatic volume and splenic volume as assessed by MRI will be summarized using descriptive statistics by analysis windows outlined in [Appendix B](#). Liver (hepatic fat fraction, [REDACTED]) and spleen MRIs will also be displayed in patient listings for all randomized patients.

### **3.8 Changes in the Planned Analysis**

Study treatment is discontinued before completing the protocol specified treatment period. The following protocol specified analysis will not be conducted at the final analysis.

1. Protocol section 10.3 “Per Protocol Set (PPS)”, in final analysis, Per Protocol Set will not be classified. All analysis endpoint will not be assessed in PPS.
2. Protocol section 10.6.3 primary efficacy analysis, patient with missing primary endpoint will be excluded from primary efficacy analysis (ANCOVA). Protocol specified imputation method and sensitivity analysis to assess the robustness of the primary analysis results will not be conducted. For secondary efficacy analysis (patients who achieve a  $\geq 40\%$  reduction in fasting triglyceride from Baseline and  $\geq 30\%$  reduction of hepatic fat fraction percent from baseline at Month 6), protocol specified statistical comparison will not be conducted, only descriptive summary will be provided. The change from baseline in fasting triglycerides, hepatic fat fraction, and HbA1c will be assessed using ANCOVA model with derived FPL based off of genetic confirmation as a stratification factor. A subset analysis will look at the change from baseline in fasting triglycerides, hepatic fat fraction, and HbA1c by gene mutation of LMNA + PPARG and no mutation. The ANOCOVA model used for this analysis will include an interaction term between treatment and FPL group
3. Protocol section 10.1.2 states that Disease burden score is one of secondary efficacy endpoint. However this patient-reported outcome is not collected in the study. Disease burden score will not be summarized.

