- All patients treated with volanesorsen who discontinue the study will have missing post-treatment discontinuation TG values multiply imputed using estimates from the placebo patients. Specifically, the copy increment from reference (CIR) approaches will be used
- Patients treated with volanesorsen who discontinue the study will have missing post-discontinuation TG values multiply imputed based on baseline TG and the imputation model for the placebo

The additional sensitivity analyses will be conducted for the primary efficacy analysis, and details of the analyses will be specified in the SAP:

- The primary analysis will be repeated in the PPS
- The primary analysis will be repeated in the subset of FAS who have a non-missing primary endpoint
- The following analyses will be conducted on both the FAS and PPS:
  - The primary analysis will be repeated to compare the percent change from Baseline to average of Weeks 8 (Day 50), 12 (Day 78) and 13 (Day 85) between treatment groups. Missing data will not be imputed
  - The primary efficacy endpoint will be analyzed using Wilcoxon rank-sum test for sensitivity analysis, and the treatment effect will be estimated using Hodges-Lehmann estimator
  - For the responder analysis described above, all patients with a missing primary endpoint will be considered as non-responders
  - The primary efficacy endpoint will also be analyzed using the nonparametric Wei-Johnson method

Secondary [REDACTED] efficacy analyses will be conducted in both the FAS and PPS, and described fully in the SAP:

- Change from Baseline in hepatic fat fraction (%) as assessed by MRI will be compared between ISIS 304801 300 mg qw and placebo groups using an ANCOVA model with baseline and the stratification factor as covariates

- Change from Baseline in HbA1c will be compared between ISIS 304801 300 mg once-weekly and placebo group using an ANCOVA model with baseline and the stratification factor as covariates

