- Proportion of patients who achieve a  $\geq 40\%$  reduction in fasting TG from Baseline and  $\geq 30\%$  reduction of hepatic fat fraction percent from baseline at Month 6 between ISIS 304801 300 mg once-weekly and placebo group will be analyzed using a logistic regression model with the randomization stratification factors, log transformed Baseline TG, and Baseline hepatic fat fraction as covariates. Missing data will be considered as informative missing for patients who discontinue the study prior to the primary analysis time point due to lack of efficacy or Adverse Events or other types of treatment failure; otherwise, missing data will be considered as non-informative missing. In the responder analysis, patients with informative missing data will be treated as non-responders. Non-informative missing data will be handled using the same multiple imputation method as the primary analysis. Analyses will also be performed in which the above primary and secondary efficacy endpoints are evaluated at the Month 3, Month 6, and Month 12 analysis time points, where applicable. The efficacy endpoints will also be evaluated at Month 15, Month 18, and Month 24 in the OLE period as appropriate.

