#### ***3.4.2.2 Secondary Endpoint 2: Change from Baseline in HbA1c***

HbA1c (%), change from baseline, and percent change from baseline will be summarized by analysis visit using descriptive statistics in FAS. They will also be summarized separately by genetic mutation category: LMNA, PPARG, or neither. Descriptive summary statistics refers to section 3.2.1. Visit includes baseline and analysis visits according to the visit window defined in [Appendix B](#).

The change in HbA1c from Baseline to Randomized Treatment Period month 3, month 6, month 9 and month 12 will be analyzed using this similar ANCOVA model as for the primary efficacy analysis

A subgroup analysis of the ANCOVA will also be run for change in HbA1c from baseline in the group of genetically confirmed patients according to the University of Chicago data for patients who consented to genetic testing or historical data for patients who did not consent, and in patients with no mutation at month 3, month 6, month 9 and month 12 respectively.

**3.4.2.3 Secondary Endpoint 3: Proportion of patients who achieve a >=40% reduction in fasting triglyceride from Baseline and >=30% reduction of hepatic fat fraction percent from baseline at Month 6**

Frequency and proportion of patients who achieve a >=40% reduction in fasting triglyceride from baseline and >=30% reduction of hepatic fat fraction from baseline at Month 6 will be displayed.

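### The SAP reduces the Month 6 composite responder endpoint to counts with no between-arm difference or interval, and states neither a denominator nor a missing-data rule for it

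*SAP*

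**What the plan says.** **Protocol 10.6.3.** The composite responder proportion "will be analyzed using a logistic regression model with the randomization stratification factors", log baseline TG and baseline hepatic fat fraction (HFF). Missing data are split in two.

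- Missing data are informative for "patients who discontinue the study prior to the primary analysis time point due to lack of efficacy or Adverse Events" or another type of treatment failure. For these, "patients with informative missing data will be treated as non-responders".
- For the rest, "Non-informative missing data will be handled using the same multiple imputation method as the primary analysis".

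The same section's list of additional sensitivity analyses has a stricter item for a responder analysis: "all patients with a missing primary endpoint will be considered as non-responders". That item is tied to the primary endpoint.

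**SAP 3.8.** Giving as its reason that treatment ended before the planned period was complete, it states for the composite that "protocol specified statistical comparison will not be conducted, only descriptive summary will be provided".

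**SAP 3.4.2.3.** All that remains is a display: "Frequency and proportion of patients who achieve a >=40% reduction in fasting triglyceride from baseline", together with the HFF criterion, at Month 6. It does not say what the proportion is a proportion of, or how a patient without a Month 6 TG or MRI value is classed.

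**Elsewhere in the SAP.** Section 3.2.2 assigns secondary efficacy endpoints to the FAS. Section 3.1 says that the protocol's imputation and sensitivity analyses will not be done. Sections 3.3.2 and 3.3.5 remove patients with a missing primary endpoint from the primary analysis, which is also an FAS analysis.

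**The concern.** There are two separate gaps.

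First, a named secondary endpoint will be reported as two proportions with nothing to compare them by. The stated reason is early end of dosing, but the same SAP still compares Month 6 TG and Month 6 HFF between arms, and those two values determine the composite.

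Second, the reader will not know what the displayed percentages mean. A proportion among patients with both Month 6 values describes those who stayed long enough to be measured. A proportion of all FAS patients counts everyone unmeasured as a failure. With about 20 patients per arm these can differ by many points. If missingness differs between arms, the choice alone can create or widen a visible gap.

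**Working it through.** The documents give no response rate, drop-out rate or power for the composite; the power statements in Protocol 10.2 and SAP 3.3.3 concern TG and liver fat. There is therefore no plan figure to reproduce.

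**Step 1: does the stated reason cover the loss?**

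| Month 6 outcome | Between-arm analysis in the SAP |
|---|---|
| TG percent change | ANCOVA repeated at Month 6 (3.3.2) |
| HFF percent change | ANCOVA at Month 6 (3.4.2.1) |
| Composite of the two | Frequency and proportion only (3.4.2.3, 3.8) |

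Data that support the first two rows support at least an exact comparison of two proportions. Sparse responders might make the covariate-adjusted logistic model unstable, but that argues for a simpler method, not for none.

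**Step 2: what the denominator does within one arm.** Inputs: N = 20 (arm size in Protocol 10.2). Assumed: r = 8 responders, and m = 2 to 8 missing (10% to 40%).

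- Observed cases: r/(N−m)
- FAS denominator, all missing as non-responders: r/N
- Ratio of the two: N/(N−m)
- Protocol rule with i informative, the rest imputed at the observed rate: [r + (m−i)·r/(N−m)]/N, shown for i = m/2

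| m | Observed cases | FAS denominator | Protocol rule, i = m/2 | N/(N−m) |
|---|---|---|---|---|
| 2 | 8/18 = 44.4% | 40.0% | 42.2% | 1.11 |
| 4 | 8/16 = 50.0% | 40.0% | 45.0% | 1.25 |
| 6 | 8/14 = 57.1% | 40.0% | 48.6% | 1.43 |
| 8 | 8/12 = 66.7% | 40.0% | 53.3% | 1.67 |

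Observed cases exceed the FAS figure by 4 to 27 points and the protocol rule by 2 to 13 points. The FAS figure lies below the protocol rule by the same 2 to 13 points. At m = 6, the protocol rule gives 57.1% if no missing value is informative and 40.0% if all are.

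**Step 3: unequal missingness (assumed counts, 20 per arm).**

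- Equal arms, 4 responders each, 8 versus 1 missing. Observed cases: 4/12 = 33.3% versus 4/19 = 21.1%, a gap of 12.3 points. FAS denominator: 20% versus 20%, no gap.
- 8 versus 1 responders, 8 versus 3 missing. Observed cases: 8/12 = 66.7% versus 1/17 = 5.9%, a difference of 60.8 points (Fisher p = 0.00086). FAS denominator: 40% versus 5%, a difference of 35 points (p = 0.0197). Both p-values are below 0.05, so here the choice changes the size of the effect and not its direction.

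**Step 4: one route to missing Month 6 values.** SAP 3.2.1 drops assessments more than 28 days after the last dose. It says so first for the primary endpoint, then for efficacy summaries and for lipid values mapped to analysis visits. The Week 25 lipid window opens on Day 149 (SAP Appendix B), and 149 − 28 = 121. A patient whose last dose falls before Day 121 therefore has no usable Month 6 TG, even after attending the Week 25 and 26 landmark visits that Protocol 8.8.1 encourages.

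**The case against.** The change is declared openly, with a reason, in the section meant for it. Both components keep their Month 6 between-arm analysis, and SAP 3.2.4 tabulates discontinuation with reasons by arm, so unequal drop-out will be visible. This stands in part. It makes the loss transparent, but it does not supply a difference for the composite, and a disposition table does not show who lacks a Month 6 TG or HFF.

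A reader might infer that the SAP revokes a missing-as-non-responder rule. The documents do not support that. The protocol's rule covers only informative missing data, tied to leaving the study before Month 3, and imputes the rest. On its wording, a patient who left for an adverse event between Month 3 and Month 6 was not an automatic non-responder. SAP 3.8 withdraws the comparison and does not mention the rule. That it falls away is inferred from the general statement in SAP 3.1, which sits in a passage on the primary measure, and from the silence of 3.4.2.3.

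A reader might also infer that the active-arm rate will be inflated, for example through platelet-related stopping. That needs an observed-case denominator, which no section states for this endpoint, and more missing data on active treatment, for which the documents give no figure. The assignment to the FAS can be read as FAS N, in which case every missing patient already counts as a failure. That reading is not secure, because the primary analysis is also assigned to the FAS and still excludes missing values.

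Finally, scoring every missing value as failure is stricter than the protocol and debatable when dosing ended early. This stands, and is why it belongs among the sensitivity analyses.

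**Conclusion.** The point holds in a limited form. It is certain from the text that the between-arm comparison is gone, that both components are still compared at Month 6, and that SAP 3.4.2.3 gives neither a denominator nor a missing-data rule. Early end of dosing does not by itself account for the first.

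A bias in the displayed proportions is conditional, not shown. With observed cases, an arm's rate rises by N/(N−m) over the FAS denominator. With FAS N there is no overstatement, and the rate can fall below the protocol rule (40.0% against 48.6% with 6 of 20 missing, half informative). The numbers rest on an arm size of 20, assumed responder and missing counts, and imputation at the observed rate. They show how much the unstated choice can matter, not what happened in this trial. A secondary endpoint is affected; the primary analysis is not.

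**What to change.** In SAP 3.4.2.3 and 3.8:

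- Report the difference in responder proportions with an exact 95% CI, labelled supportive.
- State the FAS as denominator, with at least the protocol's informative-missing patients counted as non-responders. Say how the remaining missing patients are handled. If the protocol's imputation is restored for them, the interval must be combined over imputations, and the exact interval then belongs to the analyses without imputation.
- State that a patient who fails one observed component is a non-responder even if the other is missing, since the composite requires both.
- Show the number missing TG, HFF or both at Month 6, by arm and reason.
- Give the all-missing-as-non-responder result and the observed-case result as sensitivity analyses.

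The cost is about one extra table, and the active-arm rate may look less favourable than an observed-case figure would.

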## 5 APPENDICES

### Appendix A – Data to be reviewed by DSMB

The data to be reviewed by DSMB is referenced to the CS17 DSMB Charter v1.0-Aug 6, 2015.

Data for Review 	Listings	Tables 	Figures
Demographics and Baseline Characteristics	X	Counts and summary statistics	
Disposition	Reasons for withdrawal from study	Counts overall (and by stratum as needed)	
Medical History	X		
Concomitant Medications	X		
Study Drug Exposure	Doses received and reasons for withdrawal from drug		
Protocol deviations	Deviations will be listed by type 		
Treatment Emergent AEs	X	By MedDRA system organ class, MedDRA term and severity	
Treatment Emergent Related AEs	X	By MedDRA system organ class, MedDRA term and severity	
SUSARs	Listing and narratives		
Deaths	Listing and narratives		
Patients that have reached a protocol-defined stopping rule	Listing and narratives		
Adjudicated MACE Events	Listing and narratives		
Adjudicated Acute Pancreatitis Events	Listing and narratives		
Vital Signs (SBP, DBP, HR)	X		
Lab values (clinical chemistry, coagulation, hematology, hsCRP, complement, troponin-I, HbA1c)	X		Key parameters will be graphed by value and visit for individual patients 
Urinalysis	X		Urine protein (dipstick) will be graphed by value and study day for individual patients
ECG parameters and findings	X		
Echocardiogram findings	X		

1. Additional data may be requested by DSMB and will be provided in agreed upon format
2. Summary tables will be produced as number of patients enrolled allow
3. Protocol Deviations will be listed by the following types:
  - Eligibility criteria not met
  - Study drug administration errors

- Patient not withdrawn according to protocol requirements
- Missed laboratory sample collection for safety and/or primary endpoint
- Safety end/or primary endpoint procedures that are missed or improperly conducted
- Disallowed/restricted concomitant medications
- Non-compliance to stopping rules
- Improper informed consent procedures

4. The following key parameters will be presented graphically:

- Alanine aminotransferase (ALT)
- Aspartate aminotransferase (AST)
- Alkaline phosphatase (ALP)
- BUN
- Total, direct and indirect bilirubin
- Creatinine
- Hemoglobin
- Lymphocyte, absolute
- Neutrophil, absolute
- Platelet count
- White blood cell count

**Appendix B – Efficacy measurement analysis visit window**

Efficacy Measure	Study Period	Period week	Target Day	Study Day Window
Lipid	Screening Qual Visit Randomized Treatment Period		-56 to -15	$\leq -15$
			-14 to -7	-14 to < 1
		1	1	1
		4	22	2 to 36
		8	50	37 to 64
		12	78	65 to 82
		13	85	83 to 106
		19	127	107 to 148
		25	169	149 to 173
		26	176	174 to 197
		32	218	198 to 239
		38	260	240 to 281
		44	302	282 to 323
Lipid	Open Label Extension (OLE)		50	324 to 351
			52	$\geq 352$
		4	22	1 to 36
		8	50	37 to 64
		12	78	65 to 82
		13	85	83 to 106
		19	127	107 to 148
		25	169	149 to 173
		26	176	174 to 197
		32	218	198 to 239
		38	260	240 to 281
		44	302	282 to 323
		50	344	324 to 351
		52	358	$\geq 352$

Efficacy Measure	Study Period	Period week	Target Day	Study Day Window
		56	386	373 to 400
		60	414	401 to 428
		64	442	429 to 446
		65	449	447 to 470
		71	491	471 to 512
		77	533	513 to 537
		78	540	538 to 561
		84	582	562 to 603
		90	624	604 to 645
		96	666	646 to 687
		102	708	688 to 715
		104	722	≥ 716
	Post-Treatment Follow-up	7	43	1 to 64
		13	85	≥ 65

Efficacy Measure	Study Period	Period week	Target Day	Study Day Window
MRI liver (hepatic fat fraction)	Screening		-42 to 1	≤ 14
	Randomized Treatment Period	Month 6 (25, 26)	169-176	109 to 236
		Month 12 (50, 52)	344-358	284 to 418
	Extension Open Label	Month 6 (25, 26)	169-176	109 to 236
		Month 12 (50, 52)	344-358	284 to 418

Efficacy Measure	Study Period	Period week	Target Day	Study Day Window
	Screening		-56 to -15	$\leq -15$
		1	1	1
HbA1c	Randomized Treatment Period or Open Label Extension Period	Month 3 (13)	85	55 to 115
		Month 6 (26)	176	146 to 206
		Month 9 (38)	260	230 to 290
		Month 12 (52)	358	328 to 388

